Study Product, Dose, Route, Regimen	Patients will be randomized 1:1 to ultra-high dose (IV bumetanide 12.5 mg bid) vs standard dose (IV furosemide as twice the home dose of oral daily diuretic in furosemide equivalents administered bid) for 24 hours. Participants will undergo comprehensive physiological assessment at baseline and 24 hours with short Iohexol clearance for true glomerular filtration rate, apnea hypopnea index, electrocardiography, echocardiography, serum, and urine biomarkers. Patients will be monitored for side effects including muscle cramps, new onset atrial fibrillation (AF), sustained ventricular tachycardia (VT), symptomatic hypotension (MAP<60 or systolic blood pressure <80 mmHg), development of renal insufficiency and dialysis initiation.
Duration of Administration	Patients will be on therapy for 24 hours.

Statistical Methodology	The primary efficacy endpoint is urine output over 24 hours which will be compared by T test between the two groups. Primary safety endpoint will be incident decline in creatinine estimated glomerular filtration rate by 50% over 24 hours. Key secondary endpoints include weight change, NT-proBNP change, urine output, urine sodium excretion, creatinine, and cystatin C estimated GFR changes, apnea-hypopnea index, Iohexol glomerular filtration rate, serum and urine proteomic analyses, peripheral vein pressure and echocardiographic changes over 24 hours, estimated GFR at day 7 or discharge (whichever is sooner) will each be compared by T test between the two groups.
-------------------------	---

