3.2 Secondary Objectives

The secondary objectives of this study are

- a) To demonstrate safety of ultrahigh dose diuretics at 24 hours defined as development of renal insufficiency (creatinine estimated GFR decline of 50%), and hypotension (symptomatic MAP<60 or systolic blood pressure <80 mmHg).
- b) To determine mechanistic changes in cardiac function, sleep parameters and biomarker changes in response to ultrahigh dose diuretics compared to standard dose diuretics.
- c) To compare 24 hour change creatinine and cystatin C based changes in GFR with gold standard Iohexol clearance testing of GFR among the two diuretic strategies

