In this pilot study we will therefore compare an ultra-high diuretic strategy with a conventional diuretic strategy in patients with decompensated heart failure with a primary efficacy end point of urine output at 24 hours. The primary safety endpoint will be a decline in serum creatinine estimated GFR by 50% of baseline value at 24 hours. This will be a double-blinded randomized pilot trial of ultra-high dose diuretics (IV bumetanide 12.5 mg bid for 24 hours vs IV furosemide at usual doses (twice the home dose of oral daily diuretic in furosemide equivalents administered bid). New initiation of adjunct diuretics (thiazide, SGLT2 inhibitors, acetazolamide, and spironolactone) will be discouraged during the 24-hour study period. Key secondary endpoints include weight change, NT-proBNP change, urine output, urine sodium excretion, creatinine, and cystatin C estimated GFR changes, apnea-hypopnea index, iohexol glomerular filtration rate, serum and urine proteomic analyses, peripheral vein pressure and echocardiographic changes over 24 hours, estimated GFR at day 7 or discharge (whichever is sooner) will each be compared by T test between the two groups.

4.2 Hypothesis:

Ultrahigh dose diuretic infusion will be associated with greater diuretic response and will not be associated with clinically significant decline in eGFR over 24 hours (defined as decline in creatinine estimated GFR of 50% from baseline at 24 hours).

4.3 Innovation:

1. Ultra-high dose diuretic strategies have not been compared to conventional diuretic strategies in a randomized trial
2. The use of a double-blind strategy will minimize bias in terms of diuretic adjustment and alternative therapies.
3. The measurement of serum and urine biomarkers of renal injury, peripheral vein pressure and echocardiography changes at baseline and at 24 hours will provide novel insight into the hemodynamic, renal, and cardiac response to decongestion.

4. The relationship between creatinine based GFR during non-steady state conditions such as active diuresis and extracellular volume reduction during diuresis, and true GFR measured by lohexol clearance testing has never been studied.
5. The effect of rapid diuresis on cardiac structure and function has not been well studied
6. The short-term effect of rapid volume removal on measures of sleep is unknown

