8.1.2 Enrollment, Baseline, and/or Randomization

After confirming eligibility, informed consent will be obtained. Following consent, patients will be randomized 1:1 to ultrahigh vs standard dose diuretic strategies.

Day 1 (0-24 hours)

After randomization, patients will undergo comprehensive baseline assessment including weight, echocardiogram, history, and physical examination. Initial randomized therapy will be administered at least 6 hours after last clinically administered dose of IV diuretic (or immediately if no IV diuretic has been administered in the last 6 hours). Participants will be urged to void their bladders and discard urine at baseline immediately prior to receiving study drug. All baseline testing will be performed when feasible once consent is obtained. Baseline testing will include blood sample testing for NT proBNP, creatinine, cystatin C and hematocrit. Urine collection for urine creatinine and sodium will be specifically collected timed 1-2 hours after the administration of study diuretic dose to allow estimation of urine sodium excretion. 32 ml of blood and 30 ml of urine will be stored for future analyses. Peripheral venous pressure will be recorded from existing IV lines through pressure transducer monitoring from study team.

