In addition to blood testing as above, Iohexol based GFR calculation using subcutaneously injected-Iohexol and timed samples of blood and urine to calculate GFR will be used for research with a procedure following typical inpatient practice Iohexol based GFR measurement. We will use the short Iohexol protocol with subcutaneous iothalamate injection (Time 0:T0), urine sampling at 1 hour after subcutaneous injection, with total urine volume collected over the 1-hour period (T0 to 1 hour). Urine and serum samples will be collected again approximately 45 minutes later from T60. Serum and urine samples for Iohexol will be collected at two time points after T0: i) T60 and ii) 45 minutes after T60. We will also continuously collect urine from subcutaneous injection until the end of the test, for quality control as per standard clinical practice. If Foley catheter is not present at baseline, participants will be asked to void voluntarily prior to renal study initiation with bladder scanning to confirm residual urine following bladder emptying. Ambulatory blood pressure monitoring (ABPM) will be recorded via an upper arm cuff on the non-dominant arm. Over a 48-hour period (Days 1 & 2), a blood pressure reading will be taken every 30 minutes during the day and every hour at night. Arterial stiffness will be assessed via carotid tonometry and placing a femoral and brachial blood pressure cuff on the upper thigh and upper arm. A liver ultrasound scan (Fibroscan) of the abdominal region will quantify liver elastography and potential liver disease.

Nocturnal screening for apnea-hypopnea index as a measure of sleep apnea will be performed using Watch Pat or Nox device. The Watch Pat is a non-invasive wrist monitor and will be worn overnight to test for sleep apnea. The Nox device is a portable polysomnography device to

measure sleep quality and determine sleep apnea presence. If patients have known sleep apnea, they will continue their home CPAP/BiPAP during the overnight test.

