10. INTERVENTION DISCONTINUATION

Discontinuation of the study intervention is recommended for any incapacitating and/or life-threatening side effect. Resuming the study medication will depend on an evaluation if the drug can be safely resumed. Patients may have to permanently discontinue study interventions and for this reason participation in this study if intolerable side effects persist.

At any point in time and for any reason, patients may withdraw voluntarily from participation in the study.

In the absence of any reason for premature termination as outlined above, participation will end for every patient after 6 months of trial participation.

Blood pressure will be assessed before administration of the second dose of assigned IV diuretic. In the event of symptomatic hypotension (symptomatic MAP<60 or systolic blood pressure <80 mmHg), the participant will be evaluated by the PI and study team and further dose of study medication will be suspended. The patient, PI and clinical team will be unblinded to allow the clinical team to make a determination of optimal subsequent plans of care and diuretic dosing.

Study stopping rules for safety

We will also implement Bayesian monitoring with utilization of an independent study monitor [name] who will have access to unblinded patient data as they accrue with continuous monitoring of safety. Among the high dose diuretic arm, assuming a probability of serious adverse events of 1/20 (5%) as prior information, we will monitor for 1) symptomatic hypotension (defined above) and 2) a decline in estimated GFR from 0-24 hours of >50%. Based on prior experience with this intervention, we formulated a Bayesian prior distribution for the adverse event rate p associated with this intervention, tantamount to observing 1 adverse event in 20 previous patients, or a 5% prior probability. Based on this prior, the Bayesian prior probability that the true adverse event rate exceeds 20% is only 6%. We have developed a stopping boundary, based on the Bayesian analysis of the accumulating data and the criterion that we would stop the trial if the posterior probability that the true AE rate exceeds 20% gets to 40% or more. This leads to the monitoring boundary at which point, we will pause the study and consider protocol modification and/or cessation of the study as appropriate. This decision will be discussed and made by the PIs from cardiology ([name], [name]) and nephrology ([name]) and statistician ([name])

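### The primary safety endpoint counts renal harm only through 24-hour creatinine eGFR, which usually understates a true halving; the Iohexol GFR measured on both days is not tabulated patient by patient.

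*Combined protocol and SAP*

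**What the plan says.** Section 1 (Statistical Methodology) states: "Primary safety endpoint will be incident decline in creatinine estimated glomerular filtration rate by 50% over 24 hours". Section 4.1 repeats it: "The primary safety endpoint will be a decline in serum creatinine estimated GFR by 50% of baseline value at 24 hours". Sections 3.2(a) and 4.2 also define the renal event by creatinine eGFR.

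Section 10 sets up Bayesian monitoring of the high-dose arm. It counts symptomatic hypotension and "a decline in estimated GFR from 0-24 hours of >50" percent. That sentence does not name the marker, and it asks for more than 50% where sections 1 and 4.1 say a fall of 50%.

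The protocol treats creatinine's validity here as an open question. Section 4.3, item 4, says that "The relationship between creatinine based GFR during non-steady state conditions such as active diuresis", compared with true GFR by Iohexol clearance, has never been studied. Section 3.2(c) plans to compare "24 hour change creatinine and cystatin C based changes in GFR with gold standard" Iohexol clearance. The schedule in section 8 and section 8.1.3 place Iohexol testing on Day 1 and Day 2. In section 11.5.1 (items 1.3.2.5 and 1.5.1) Iohexol GFR is a secondary outcome, analysed by linear regression as a between-group difference in 24-hour change.

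**The concern.** After a sudden drop in GFR, serum creatinine climbs to its new level over days. At 24 hours an eGFR computed from it still reflects part of the old function, so a threshold of 50% applied then asks for more than a 50% true fall in most patients.

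The mean Iohexol comparison does not fill the gap. If GFR halved in 3 of 10 high-dose patients and was unchanged in the rest, the arm mean would move by 3 × 50% / 10 = 15% of baseline, with no sign that individuals had crossed the sponsor's own harm threshold. Section 4.4 intends the safety result to support a phase III trial, so a count of zero or one renal event could carry more reassurance than the data justify.

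**Working it through.** **1. The plan's own monitoring figures.** Section 10 gives a prior worth 1 event in 20 patients and a prior probability of 6% that the event rate exceeds 20%. Beta(2,20) gives 5.8%; Beta(1,19) gives 1.4% and does not match. Beta(2,20) also returns the tabulated posteriors: 46.0% for 3 events in 3 patients (stated 46), 42.1% for 3 in 4 (stated 42), 42.8% for 4 in 9 (stated 43). With the 40% cutoff, the boundary is 3 events at 3–4 patients, 4 at 5–9 and 5 at 10.

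**2. What creatinine shows at 24 hours.** The documents give no eGFR equation, distribution volume or baseline GFR distribution, so these are assumptions. Section 6.2 excludes only stage V kidney disease and dialysis, so baseline GFR 30 to 60 mL/min is eligible. Assume one compartment of volume V, steady state at baseline, constant creatinine generation, and eGFR proportional to creatinine^−a. If GFR is multiplied by f at dose 1, then with K = GFR × 1.44 L/day:

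C(24 h)/C(0) = 1/f − (1/f − 1) × exp(−f × K / V); apparent fall = 1 − [C(24 h)/C(0)]^−a.

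Example: GFR 45, V = 48 L, f = 0.5. K = 64.8; exp(−0.5 × 64.8/48) = 0.509; ratio = 2 − 0.509 = 1.491; with a = 1.2 the apparent fall is 38.1%.

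Apparent fall after a true halving, no fluid loss:

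| V, exponent | GFR 30 | GFR 45 | GFR 60 |
|---|---|---|---|
| 36 L, 1.2 | 36.0% | 42.8% | 47.1% |
| 48 L, 1.2 | 31.0% | 38.1% | 42.8% |
| 48 L, 1.0 | 26.6% | 32.9% | 37.2% |
| 60 L, 1.0 | 23.2% | 29.4% | 33.9% |

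Fluid loss concentrates creatinine. Section 10 reports urine output of 10.0 with very high dosing; taken as litres over 72 hours, that is 10.0/3 = 3.3 L per day. Letting V shrink by 3.3 L over the day moves the range to 26.8% (60 L, exponent 1.0, GFR 30) through 50.6% (36 L, exponent 1.2, GFR 60).

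**3. Where a halving is caught.** With a = 1.2 the creatinine ratio must reach 2^(1/1.2) = 1.782. At GFR 60 without fluid loss this needs V below about 28 L. With 3.3 L lost it needs V below about 38, 30 and 23 L at GFR 60, 45 and 30. A step fall at dose 1 is the case most favourable to creatinine: if GFR declines linearly to half over the 24 hours, the apparent fall is 18 to 35% (V 30 to 50 L, exponent 1.2).

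**4. Noise in Iohexol.** With lognormal error, the chance that a true ratio f is read as a fall of more than 50% is Φ(ln(0.5/f) / (√2 × CV)). For a stable patient (f = 1) this is 0.7% at an assumed CV of 20% and 5.1% at 30%. For an exact halving it is 50% at any CV.

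**5. If Iohexol falls also counted toward the boundary.** Event rate = 1 − (1 − h)(1 − r × s), where h is the hypotension rate, r the share with renal harm and s the chance that the harm is counted. Pause probabilities are exact over 10 high-dose patients.

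- *Harm present* (30% true halvings, 10% hypotension, V = 48 L, exponent 1.2, creatinine CV 5%): creatinine alone gives about 1 to 2% across GFR 30 to 60. Adding Iohexol gives, at GFR 30, a rate of 1 − 0.90 × (1 − 0.30 × 0.50) = 23.5% and a pause probability of 15%; the range across GFR 30 to 60 is 15 to 16%.
- *No halving, but a uniform 30% true fall* (5% hypotension, Iohexol alone as the renal marker): at CV 20%, s = 11.7%, rate = 1 − 0.95 × 0.883 = 16.1%, pause probability 4.9%. At CV 30%, s = 21.4%, rate 25.3%, pause probability 18%.

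**The case against.** The strongest reply is that renal safety does not rest on this endpoint alone. Section 9.5 counts a worsening abnormal laboratory finding as an adverse event. Section 9.6 has out-of-range laboratory values reviewed quarterly and serious events per occurrence. Section 9.3 checks the renal panel at least twice, and section 10 gives an independent monitor unblinded data as they accrue. A reader might infer that an individual Iohexol fall would go wholly unseen; these sections do not support that. What remains is that none of them defines an Iohexol fall as a renal event or has it tabulated.

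A reader might also infer that the boundary is written on creatinine. Section 10 says only estimated GFR, and cystatin C is measured in real time (section 12.2). Creatinine is the natural reading, because every definition of the renal event uses it, but section 10 should say so.

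A third reply is that sections 4.1 and 10 regard transient creatinine changes as benign, and that section 10 reports mean creatinine changes of −0.03 and −0.02 in observational data. Section 4.1 speaks of small changes, whereas the sponsor itself chose 50% as the harm threshold. A mean creatinine change cannot exclude individual falls.

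The objection to counting Iohexol toward the boundary has real force. Moderate falls plus noise could trigger pauses, the 1-in-20 prior was not built for that event, and a pre-dose baseline is not assured. Section 8.1.2 says "All baseline testing will be performed when feasible once consent is obtained" and allows dosing "or immediately if no IV diuretic has been administered in the last 6 hours", while the test takes about 60 + 45 = 105 minutes.

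**Conclusion.** The point holds as a cheap improvement. The primary safety endpoint, and the boundary if it uses creatinine, will usually miss a true sudden halving at baseline GFR 30 to 60: the apparent fall is 23 to 47%, or 27 to 51% with 3.3 L of fluid loss. This rests on assumed kinetics, volumes and exponents. It is not absolute, since small patients near GFR 60, or those losing much fluid, can cross 50%.

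Nothing in the documents shows that halvings will occur; the 30% rate used above is only an illustration. Nor do the documents establish that the boundary must be widened. That step would raise the pause probability from about 1–2% to about 15% in the harm scenario, but would produce pauses of about 5 to 18% in a scenario with no halving at all. The supported conclusion is narrower: the plan should report individual falls on the reference measurement that it already collects.

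**What to change.** - Keep the creatinine endpoint, the 50% threshold and the section 10 boundary as they are.
- Prespecify in section 11.5.1 a table by arm, beside the primary safety endpoint, of individual Iohexol GFR falls of the sponsor's threshold size from Day 1 to Day 2, with cystatin C eGFR falls alongside. Flag Iohexol values whose baseline was not completed before dose 1, and report the number missing.
- Send these results to the independent unblinded monitor as supporting information as they become available.
- In section 10, name the eGFR marker and use one threshold throughout, either a fall of 50% or a fall of more than 50%.
- Reconcile the tracer in section 8.1.2, which reads "We will use the short Iohexol protocol with subcutaneous iothalamate injection".
- The sponsor should decide, and record, whether Iohexol falls also count toward the boundary. If so, it should confirm that the prior suits the wider event.

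No new test is needed. The cost is a little tabulation and routing of results, and the noise in Iohexol: a false fall of more than 50% in 0.7% (CV 20%) to 5.1% (CV 30%) of stable patients, which the table should state as a caveat.

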
11. STATISTICAL CONSIDERATIONS

11.1 General Design Issues and possible approaches to address them

Muscle cramps is a possible side effect of high dose bumetanide infusions and may limit continuation of bumetanide therapy. In the event of severe muscle pain, the dose of subsequent blinded infusion can be decreased to half the infusion to minimize pain with analgesic use as needed. If side effect is severe requiring change in therapy despite electrolyte correction and decrease in diuretic dosing, patients will be unblinded with subsequent therapy provided as per clinical practice. Providers are variable in adjunct strategies with vasodilators, inotropes, and adjunct diuretics during management of acute decompensated heart failure. We will exclude patients with anticipated initiation or use of inotropes at baseline, and adjunct thiazide diuretics will be discouraged for the 24 hours during the study protocol. We will only recruit patients with

stable respiratory status without use of non-invasive or invasive mechanical ventilation to minimize need for rescue therapies.

11.2 Sample Size and Randomization

This is a pilot study and sample size of 20 is selected based on feasibility to determine probably efficacy and safety to guide design of a pivotal trial. The dose separation between ultrahigh and standard dose diuretics is higher than has previously been tested and there is no data on diuretic differences at such high doses.

11.2.1 Treatment Assignment Procedures

Randomization will be performed 1:1 after consent without block randomization or stratification.

11.3 Interim Analyses and Stopping Rules

Given small sample size, no interim analyses are planned

11.4 Outcome Measures

11.4.1 Primary trial objective

To determine the diuretic effect of ultrahigh compared to standard diuretic measures

11.4.1.1 Primary outcome measures

Urine output at 24 hours

11.4.2 Secondary trial objective

Determine renal, cardiac, and systemic effects of ultra-high dose compared to standard diuretic regiments

11.4.2.1 Outcome measures

Key secondary endpoints include weight change, NT-proBNP change, urine output, urine sodium excretion, apnea-hypopnea index, Iohexol glomerular filtration rate, peripheral vein pressure and echocardiographic changes over 24 hours

11.5 Data Analyses

11.5.1 Statistical Considerations and Methodology

1.1 Overview: This is a single-site, randomized, double-blind, parallel-group clinical trial in acute decompensated heart failure patients with volume overload requiring hospitalization. Patients will be randomized in a 1:1 fashion to either ultra high dose intervention with intravenous bumetanide 12.5 mg bid over 24 hours (Group 1) or standard dose intervention with intravenous furosemide as twice the home dose of oral diuretic in furosemide equivalents administered bid over 24 hours (Group 2).

1.2 Primary and Secondary Objectives

- 1.2.1 Primary objective: To determine the diuretic effect of ultra high compared to standard diuretic measures.
- 1.2.2 Secondary objective: To determine renal, cardiac, and systemic effects of ultra high dose compared to standard diuretic regimens.

1.3 Primary and Secondary Outcomes

- 1.3.1 Primary outcome: urine output at 24 hours after initiation of intravenous diuretic.
- 1.3.2 Secondary outcomes: changes in the following measures over 24 hours after initiation of intravenous diuretic:
 - 1.3.2.1 Body weight
 - 1.3.2.2 NT-proBNP change
 - 1.3.2.3 Urine sodium excretion
 - 1.3.2.4 Apnea-hypopnea index
 - 1.3.2.5 Iohexol glomerular filtration rate
 - 1.3.2.6 Peripheral vein pressure
 - 1.3.2.7 Echocardiographic measures of cardiac output, estimated RV systolic pressure, RA pressure, LA strain, LV and RV global longitudinal strain, E/e'

1.4 Primary Analysis

- 1.4.1 The primary analysis will be to compare urine output at 24 hours after initiation of intravenous diuretic. All patients meeting eligibility criteria who provide informed consent, are randomized, and receive any dose of intravenous diuretic will be included in the primary analysis based on intention-to-treat (ITT) principles. The difference in 24-hour urine output between groups will be estimated using a linear regression model; 95% confidence intervals will be constructed using t-based methods. A p-value less than 0.050 will be considered statistically significant.

